6.3.3.3 Mandatory dose modifications and recommended clinical management guidelines for skin rash

Guidelines for dose modification and management of skin rash considered to be related to study treatment by the investigator are provided in [Table 6-11](#).

Table 6-11 Mandatory dose modifications and recommended clinical management guidelines for rash

Rash Events (NCI-CTCAE v4.03)		
Grade	Recommended adverse event management guidelines	Mandatory dose modification requirements
Grade 1: Rash covering < 10% body surface area	
 Initiate prophylactic and symptomatic treatment measures. Consider use of topical corticosteroids or urea containing creams in combination with oral antipruritics or moderate strength topical steroid (hydrocortisone 2.5% cream or fluticasone propionate 0.5% cream) Reassess after 2 weeks 	
 Continue PDR001/placebo, dabrafenib and trametinib at the same dose.
Grade 2: 10-30% of body surface area	
 If tolerable, as per Grade 1 	
 If tolerable, continue PDR001/placebo, dabrafenib and trametinib at the same dose.

Rash Events (NCI-CTCAE v4.03)		
Grade	Recommended adverse event management guidelines	Mandatory dose modification requirements
	
 If intolerable, initiate systemic steroids (0.5 to 1 mg/kg/day prednisone or equivalents) If symptoms persist or recur consider skin biopsy. 	
 If intolerable: 
1st occurrence
 
 Interrupt PDR001/placebo, dabrafenib and trametinib until ≤ Grade 1, and then reinstate PDR001 treatment (after appropriate steroid tapering) and reduce dabrafenib and trametinib to the next dose level per Table 6-7. Re-escalation of the subject's dose is recommended if criteria in Section 6.3.2 are met. AE resolution to ≤ Grade 1 or baseline must occur within a period of 12 weeks since a Grade 3 event has been identified, otherwise PDR001 must be permanently discontinued.
Grade 3: More than 30% of body surface area	
 Obtain a skin biopsy and dermatology consult. Initiate therapy with high dose steroids (1 to 2 mg/kg/d prednisone or equivalents) 	
1st occurrence
 
 Interrupt PDR001/placebo, dabrafenib and trametinib until ≤ Grade 1, and then reinstate PDR001 treatment (after appropriate steroid tapering), and reduce dabrafenib and trametinib to the next dose level per Table 6-7. Re-escalation of the subject's dose is recommended if criteria in Section 6.3.2 are met. AE resolution to ≤ Grade 1 or baseline must occur within a period of 12 weeks since a grade 3 event has been identified, otherwise PDR001 must be permanently discontinued. 
2nd occurrence
 
 Permanently discontinue PDR001/placebo. Interrupt dabrafenib and trametinib until ≤ Grade 1 or baseline. Once recovered, reduce dabrafenib and trametinib to the next dose level per Table 6-7. Re-escalation of the subject's dose is recommended if criteria in Section 6.3.2 are met. 
3rd occurrence
 
 Interrupt dabrafenib and trametinib until ≤ Grade 1 or baseline. Once recovered, reduce dabrafenib and trametinib to the next dose level per Table 6-7. Re-escalation of the

Rash Events (NCI-CTCAE v4.03)		
Grade	Recommended adverse event management guidelines	Mandatory dose modification requirements
		subject's dose is recommended if criteria in Section 6.3.2 are met.
		4th occurrence
		
 Permanently discontinue PDR001/placebo, dabrafenib and trametinib.
Grade 4: Life-threatening	
 Same as Grade 3 	
 Permanently discontinue PDR001/placebo, dabrafenib and trametinib.

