6.1.1.4 PDR001 or placebo administration

PDR001 or placebo will be administered via intravenous infusion over 30 minutes (up to 2 hours, if clinically indicated) once every 4 or 8 weeks as determined in part 1. Subjects should be provided instructions to notify study personnel if symptoms of infusion reaction occur after any PDR001 infusion. The dose may be interrupted up to 12 weeks. The safety assessments as outline in [Section 7](#) should be performed.

Study visits with scheduled PK sampling should be scheduled in the morning so that a pre-dose PK blood sample can be collected. Scheduling these visits in the morning is especially important for Cycle 1 Day 1 and Cycle 3 Day 1 during which a post-dose (end-of-infusion) PK sample is to be collected.

Following final PFS analysis, and subsequent unblinding, placebo administrations to those patients randomized to the placebo arm will stop.

If there is a delay due to a logistical issue for administering PDR001 due to COVID-19 pandemic then the participant should receive the infusion once it is feasible while continuing

therapy with dabrafenib and trametinib. Home delivery/administration is generally not recommended.

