6.3.1 General dose modification instructions for PDR001 or placebo

No dose reductions are allowed for PDR001. Dose interruption for PDR001/placebo includes delaying or withholding the treatment for any reason as well as an interruption of treatment during an infusion. Subjects with adverse events suspected to be related to PDR001 or placebo including those of potential immune-mediated etiology (irAE) (see definition in [Section 6.3](#)) must be permanently discontinued from PDR001 or placebo if (1) the AE doesn't recover to ≤ Grade 1 or baseline within 12 weeks and/or (2) the dose of steroids (for the management of irAE) remains > 10 mg/day prednisone or equivalent for >12 weeks.

The 12 week timeframe will begin from the time the irAE reaches a grade that leads to PDR001/placebo interruption.

Subjects who discontinue the study for a study related adverse event or an abnormal laboratory value must be followed as described in [Section 7](#).

6.3.2 General dose modification instructions for dabrafenib and trametinib:

[figure not shown]
If treatment related toxicities occur that are specific to combination treatment of dabrafenib and trametinib, then both treatments should be simultaneously dose reduced, interrupted or discontinued with the exceptions shown below:

Exception where dose modification is necessary for **only dabrafenib**:

- Uveitis ([Table 6-25](#))

Exception where dose modifications are necessary for **only trametinib**:

- Retinal vein occlusions (RVO) ([Table 6-25](#)) and retinal pigment epithelial detachment (RPED) ([Table 6-26](#))
- Left ventricular ejection fraction (LVEF) reduction ([Table 6-22](#))

If a subject’s dose of dabrafenib and trametinib has been reduced per the dose modification instructions, re-escalation of the subject’s dose is recommended provided the following criteria are met:

- a period of 4 weeks of treatment has passed since restarting dosing at the lower dose level and there is no recurrence of the AE
- the subject is deriving clinical benefit

For dabrafenib and/or trametinib related adverse events: if following an interruption of dabrafenib and trametinib, an AE doesn’t recover to ≤ Grade 1 or baseline within 4 weeks, dabrafenib and trametinib must be discontinued.

6.3.3 Dose modification and management guideline for adverse events common to PDR001, dabrafenib and trametinib

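### Table 6-11 times the 12-week PDR001 stop for intolerable Grade 2 rash from a Grade 3 event, so the cell's own stop never starts for a rash that stays at Grade 2

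*Protocol*

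**What the plan says.** Table 6-11 (Protocol Section 6.3.3.3) covers "management of skin rash considered to be related to study treatment by the investigator". For a first occurrence of intolerable Grade 2 rash, the mandatory column interrupts all three drugs until the rash is Grade 1 or lower, and "then reinstate PDR001 treatment (after appropriate steroid tapering) and reduce dabrafenib and trametinib" by one level. It then requires resolution "within a period of 12 weeks since a Grade 3 event has been identified, otherwise PDR001 must be permanently discontinued".

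The Grade 3 row of the same table carries the same sentence: "within a period of 12 weeks since a grade 3 event has been identified, otherwise PDR001 must be permanently discontinued".

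Three general provisions bear on the point:

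- Section 6.3.1 sets a 12-week limit to recovery, after which PDR001/placebo stops permanently. It applies to "Subjects with adverse events suspected to be related to PDR001 or placebo including those of potential immune-mediated etiology", and on timing it says: "The 12 week timeframe will begin from the time the irAE reaches a grade that leads to" interruption of PDR001/placebo.
- Section 6.3.2 applies to events related to dabrafenib and/or trametinib. If there is no recovery "within 4 weeks, dabrafenib and trametinib must be discontinued". It does not mention PDR001.
- Section 6.1.1.4 says of PDR001/placebo: "The dose may be interrupted up to 12 weeks". It gives no causality condition and does not say what follows at 12 weeks.

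**The concern.** In this cell PDR001/placebo is interrupted at Grade 2, but the time limit on recovery is tied to Grade 3. A rash that becomes intolerable at Grade 2 and never spreads further gives the clock no start, so the mandatory permanent stop in the cell cannot be triggered.

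At stake is whether PDR001 may be restarted after a rash that took more than 12 weeks to resolve. The table is the place a site would look first, because Table 6-8 sends skin rash to Table 6-11.

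**Working it through.** No sample size, power or error-rate figure is involved, so the check is a comparison of texts and a count.

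**1. Does the sentence do any work in the Grade 2 cell?** Table 6-11 puts rash on 10–30% of body surface in Grade 2 and rash on more than 30% in Grade 3.

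- Rash stays at Grade 2: no Grade 3 event exists, so the clock has no start.
- Rash worsens to Grade 3: the Grade 3 row applies, with its own limit from the Grade 3 event.

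In neither case does the sentence in the Grade 2 cell add a rule.

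**2. How do the other rows start the clock?** Rows in Section 6.3.3 that state a 12-week PDR001 clock:

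| Table | Row | Clock starts at |
|---|---|---|
| 6-9 diarrhea/colitis | Grade 3 | own event |
| 6-11 rash | Grade 2 intolerable | **Grade 3 event** |
| 6-11 rash | Grade 3 | own event |
| 6-12 renal | Grade 2 | own event |
| 6-12 renal | Grade 3 | own event |
| 6-13 pneumonitis | Grade 1 | own event |
| 6-13 pneumonitis | Grade 2 | own event |
| 6-14 encephalitis | Grade 2 | own event |
| 6-15 endocrine | symptomatic | own event |
| 6-17 neutropenia | Grade 3–4 | own event |
| 6-17 thrombocytopenia | Grade 3 with bleeding, or Grade 4 | own event |
| 6-18 other AEs | Grade 2 intolerable or Grade 3 | own event |
| 6-19 other AESI | Grade 2 | own event |
| 6-19 other AESI | Grade 3 | own event |

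The total is 14 rows: 13 start at their own event and 1 at a higher grade. The closest parallel is Table 6-18, which also acts on intolerable Grade 2 and runs its clock from the intolerable Grade 2 or Grade 3 event.

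**3. When does a PDR001 stop fall?** Take a first rash that becomes intolerable at Grade 2 at week 0, never reaches Grade 3, and has not recovered to Grade 1 or baseline by week 12.

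| Rule | Suspected related to PDR001/placebo | Attributed only to dabrafenib/trametinib |
|---|---|---|
| Table 6-11 cell as written | no date | no date |
| Section 6.3.1 | permanent stop at week 12 | does not apply |
| Section 6.3.2 | – | dabrafenib and trametinib stop at week 4; silent on PDR001 |
| Section 6.1.1.4 | interruption limited to 12 weeks | interruption limited to 12 weeks |
| Table 6-11 cell with the fix | permanent stop at week 12 | permanent stop at week 12 |

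The right-hand column lies within the scope of Table 6-11, because Section 6.1 defines study treatment as PDR001 or placebo together with dabrafenib and trametinib.

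**4. How many subjects could be affected?** The Amendment 7 rationale gives 88 subjects on treatment in part 3, 2 in part 1 and 1 in part 2: 88 + 2 + 1 = 91. This is only a ceiling. Placebo had been stopped and the number still on PDR001 is not given. Within it, only a first intolerable Grade 2 rash unresolved at 12 weeks is touched.

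**The case against.** The strongest reply is that the case that matters is already covered. For a rash suspected to be related to PDR001/placebo, Section 6.3.1 gives the 12-week permanent stop, starting at the grade that caused the interruption; it also stops PDR001 if steroids for an immune-related event stay above 10 mg/day for more than 12 weeks. The table does not relax that rule, and nobody receives PDR001 while the rash is above Grade 1. All of this stands, and it keeps the point small.

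Further replies have partial force:

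- *Not stopping PDR001 for a rash not blamed on it matches the general rule.* That is true of Section 6.3.1. However, the Grade 3 row of Table 6-11 applies its stop to any rash related to study treatment, and the Grade 2 cell is plainly meant to do likewise.
- *Table 6-18 covers non-hematologic events without excepting rash.* It could serve as a fallback, but Table 6-8 directs rash to Table 6-11, so it does not repair the cell.
- *The other rows are not all clean.* The Grade 1 pneumonitis row sets a target of Grade 1 or baseline, which is met at onset. The neutropenia and thrombocytopenia clocks appear only under the second occurrence. The Grade 2 rows for diarrhea/colitis, liver enzymes and hand-foot reaction state no clock at all. This is correct, and in practice the rash cell sits where those three rows sit. But silence leaves the general rule in charge, whereas this cell states a different trigger.
- *The study was near its end at Amendment 7.* The five-year follow-up of the last randomized subjects falls in mid-2023, counting from a last first visit on 8 June 2018 and a last first treatment on 11 July 2018. This limits the practical benefit; it does not make the text right.

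**Conclusion.** The concern holds. The 12-week stop in the intolerable Grade 2 cell of Table 6-11 cannot operate for a rash that stays at Grade 2, and its trigger contradicts Section 6.3.1 and the 13 other rows that state such a clock. The wording matches the Grade 3 row and may have been carried over, although the protocol does not say so. No reason is given for treating rash differently.

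The consequence is minor. The protocol as a whole still stops PDR001 at week 12 when the rash is suspected to be related to PDR001/placebo. What remains is possible rechallenge after week 12 by a site that uses the table alone, or when the rash is attributed only to dabrafenib/trametinib. This rests on a literal reading of the cell and on Section 6.1.1.4 not itself requiring permanent discontinuation. Sample size, power, type I error and endpoints are untouched.

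**What to change.** In the intolerable Grade 2, first-occurrence cell of Table 6-11, change the start of the 12-week period from a Grade 3 event to *the intolerable Grade 2 event*. Leave the Grade 3 row as it is. The cell then agrees with Section 6.3.1 and with Table 6-18.

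The change is a few words in one cell and has no effect on data, endpoints or analysis. Because the table is mandatory, the change would presumably go through an amendment with ethics committee approval, as Amendment 7 did, so it is best carried with the next amendment made for other reasons.

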recorded on the Dosage Administration Record eCRF. Three dose reductions for dabrafenib and two dose reductions for trametinib are permitted. If more dose reductions of dabrafenib and trametinib are required, the subject must be permanently discontinued from that specific study treatment. Dose modification steps for PDR001 or placebo, dabrafenib and trametinib in [Table 6-7](#) must be followed for the AEs presented in [Section 6.3](#).

[Table 6-8](#) provides a list of AEs of special interest and relevant sections where detailed dose modification and management requirements for relevant AEs and/or irAEs can be found. All AEs are to be graded according to NCI-CTCAE v4.03, unless otherwise specified. Investigators should refer to the current PDR001 Investigator's Brochure and the dabrafenib and trametinib local prescribing information for additional information regarding the background of each drug and the management of other AEs or potential safety-related issues not specifically mentioned in this protocol.

Trial participants with confirmed active COVID-19 infection or presenting with symptoms indicative of COVID-19 infection which may include but not limited to fever, cough, difficulty breathing, sore throat, pneumonia, loss of sense of smell, or taste or feeling unwell with flu like symptoms may interrupt study treatment based on the risk benefit assessment; in case of suspected COVID-19 infection, testing for COVID-19 is recommended as per local guidelines.

Should a patient require treatment for COVID-19 infection, the investigator should assess the risks and benefits of continued study drug treatment during this time. The investigator may consider holding study treatment until the patient is stable to restart because of potential drug to drug interaction. Additionally, the concomitant medications are to be documented in the relevant eCRF.

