Trial participants who have been exposed to someone infected by COVID-19 and/or who develop symptoms indicative of potential COVID-19 infection (see above) should contact the Investigator and discuss the next steps; these may include self-quarantine, or may require further testing/follow-up as appropriate. Administration of the study treatment may be delayed based on the risk benefit assessment until the trial participant completes the quarantine and remains asymptomatic and/or COVID-19 infection has been ruled out. Investigators are recommended to follow the local health authority guidelines for prevention against COVID-19.

[figure not shown]
[figure not shown]

Table 6-7 Dose modification steps for PDR001/placebo, dabrafenib and trametinib

Dose modification for PDR001 or placebo ^a				
	Starting dose level	Dose level - 1		
PDR001 or placebo	400 mg Q4W 400 mg Q8W (only if DL-1a is determined to be the dose regimen)	Not applicable		
Dose reduction for dabrafenib ^{a, b}				
	Starting dose level	Dose level - 1	Dose level - 2	Dose level - 3
Dabrafenib	150 mg BID (300 mg/day)	100 mg BID (200 mg/day)	75 mg BID (150 mg/day)	50 mg BID (100 mg/day)
Dose reduction for trametinib ^{a, b}				
	Starting dose level	Dose level - 1	Dose level - 2	Dose level - 3
Trametinib	2 mg QD	1.5 mg QD	1.0 mg QD	-
Q4W: once in every 4 weeks; BID: twice daily; QD: once daily				
^a . Dose modification should be based on the worst toxicity demonstrated at the last dose.				
^b . Dose reduction below 50 mg BID for dabrafenib and 1.0 mg QD for trametinib are not allowed.				

Table 6-8 Reference of AEs and toxicity management guidelines

Adverse Events	PDR001	dabrafenib	trametinib	Guideline
Diarrhea/colitis	X	X	X	Section 6.3.3.1 Table 6-9.
Abnormal liver enzyme test	X	X	X	Section 6.3.3.2 Table 6-10.
Skin rash	X	X	X	Section 6.3.3.3 Table 6-11.
Serious skin reaction	X	X	X	Section 6.3.3.4
Nephritis	X	X	X	Section 6.3.3.5 Table 6-12
Pneumonitis	X	X	X	Section 6.3.3.6 Table 6-13
Encephalitis	X	X	X	Section 6.3.3.7 Table 6-14
Endocrine events	X	X	X	Section 6.3.3.8 Table 6-15
Hand foot skin reaction	X	X	X	Section 6.3.3.9 Table 6-16
Neutropenia and thrombocytopenia	X	X	X	Section 6.3.3.10 Table 6-17
Adverse events including abnormal laboratory related AEs	X	X	X	Section 6.3.3.11 Table 6-18
Asymptomatic amylase and/or lipase elevation	X	X	X	Section 6.3.3.11 Table 6-18
Others	X	X	X	Section 6.3.3.12 Table 6-19
Infusion reaction and cytokine release syndrome	X			Section 6.3.4 Table 6-20

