Grade 3 (Creatinine > 3.0 to < 6 \times ULN)	
 Monitor creatinine every 1 to 2 days. Start 1 to 2 mg/kg/day prednisone equivalents Consult with nephrologist. Promote hydration and cessation of nephrotoxic drugs. 	
1st occurrence:
 
 Interrupt PDR001/placebo, dabrafenib and trametinib until \leq Grade 1 or baseline and then reinstate PDR001 then reduce dabrafenib and trametinib to the next lower dose per Table 6-7. Re-escalation of the subject's dose is recommended if criteria in Section 6.3.2 are met. AE resolution to \leq Grade 1 or baseline must occur within a period of 12 weeks since the Grade 3 event has been identified, otherwise PDR001/placebo must be permanently discontinued 
2nd occurrence:
 
 Permanently discontinue PDR001/placebo. Interrupt dabrafenib and trametinib until \leq Grade 1 or baseline and then reduce dabrafenib and trametinib to the next lower dose per Table 6-7. Re-escalation of the subject's dose is recommended if criteria in Section 6.3.2 are met. 
3rd occurrence:

NCI-CTCAE v4.03		
Grade	Recommended adverse event management guidelines	Mandatory dose modification requirements
Grade 4: Creatinine > 6× ULN	
 Monitor creatinine daily. Initiate steroids with 1 to 2 mg/kg/day prednisone equivalents Consult with specialist and recommend renal biopsy. Promote hydration and cessation of nephrotoxic drugs. 	
 Interrupt dabrafenib and trametinib until ≤ Grade 1 or baseline and then reduce dabrafenib and trametinib to the next lower dose per Table 6-7. Re-escalation of the subject's dose is recommended if criteria in Section 6.3.2 are met. 
4th occurrence:
 
 Permanently discontinue dabrafenib and trametinib. Permanently discontinue PDR001/placebo, dabrafenib and trametinib.

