Grade 2: Painful erythema and swelling of the hands or feet and/or discomfort affecting the subject's normal activities	
 Recommend topical therapy for symptomatic relief 	
 Continue treatment and if no improvement within 7 days, see below. No improvement within 7 days or 2nd or 3rd occurrence: 
 Interrupt PDR001/placebo, dabrafenib and trametinib until toxicity resolves to ≤ Grade 1 or baseline. Reduce dabrafenib and trametinib at the next lower dose per Table 6-7. Re-escalation of the subject's dose is recommended if criteria in Section 6.3.2 are met. 
4th occurrence:
 
 Discontinue PDR001/placebo, dabrafenib and trametinib.
Grade 3: Moist desquamation, ulceration, blistering or severe pain of the hands or feet, or severe discomfort that causes the subject to be unable to work or perform activities of daily living	
 Recommend topical therapy for symptomatic relief 	
1st occurrence:
 
 Interrupt PDR001/placebo, dabrafenib and trametinib until toxicity resolves to ≤ Grade 1 or baseline. Once recovered, reinstate PDR001/placebo, and reduce dabrafenib and trametinib to the next dose level per Table 6-7. Re-escalation of the subject's dose is recommended if criteria in Section 6.3.2 are met. 
2nd occurrence:
 
 Interrupt PDR001/placebo, dabrafenib and trametinib until toxicity recovers to ≤ Grade 1 or baseline. 
 Once recovered, reinstate PDR001/placebo, and reduce dabrafenib and trametinib to the next dose level per Table 6-7. Re-escalation of the subject's dose is recommended if criteria in Section 6.3.2 are met. 
3rd occurrence:
 
 Discontinue PDR001/placebo, dabrafenib and trametinib.

[figure not shown]

6.3.3.10 Mandatory dose modifications and recommended clinical management guidelines for neutropenia and thrombocytopenia

Guidelines for dose modification for neutropenia and thrombocytopenia suspected to be related to study treatment by the investigator are provided in [Table 6-17](#).

[figure not shown]
Table 6-17 Mandatory dose modifications and recommended clinical management guidelines for neutropenia and thrombocytopenia

Neutropenia and thrombocytopenia suspected AEs (NCI-CTCAE v4.03)		

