Grade	Recommended adverse event management guidelines	Mandatory dose modification requirements
Neutropenia		
Grade 1, 2	NA	
 Continue PDR001/placebo, dabrafenib and trametinib at the same dose.
Grade 3, 4	
 Monitor blood test more frequently (every 7 days for Grade 3, and 3-5 days for Grade 4). 	
1st occurrence:
 
 Interrupt PDR001/placebo, dabrafenib and trametinib until toxicity recovers to \leq Grade 2 or baseline. 
 Restart PDR001/placebo at the same regimen, and reduce dabrafenib and trametinib at the next dose level. Re-escalation of the subject's dose is recommended if criteria in Section 6.3.2 are met. 
2nd occurrence:
 
 Interrupt PDR001/placebo, dabrafenib and trametinib until toxicity recovers to \leq Grade 2 or baseline. 
 Restart PDR001/placebo at the same regimen, and reduce dabrafenib and trametinib at the next dose level. Re-escalation of the subject's dose is recommended if criteria in Section 6.3.2 are met. AE resolution to \leq Grade 2 or baseline must occur within a maximum period of 12 weeks since Grade 3 or 4 event has been identified, otherwise PDR001/placebo must be permanently discontinued. 
3rd occurrence:
 
 Permanently discontinue PDR001/placebo and interrupt dabrafenib and trametinib until toxicity recovers to \leq Grade 2 or baseline.

Neutropenia and thrombocytopenia suspected AEs (NCI-CTCAE v4.03)

Grade	Recommended adverse event management guidelines	Mandatory dose modification requirements
Febrile Neutropenia	
 Apply Institutional guidelines 	
 Once recovered, reduce dabrafenib and trametinib to the next dose level. Re-escalation of the subject's dose is recommended if criteria in Section 6.3.2 are met. 
4th occurrence:
 
 Permanently discontinue dabrafenib and trametinib 
 Follow modification guide for neutropenia Grade 4 (above).
Thrombocytopenia		
Grade 1, 2, 3 without clinically significant bleeding	
 Grade 3: monitor blood test more frequently (every 7 days) 	
 Continue PDR001/placebo, dabrafenib and trametinib at the same dose.

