6.3.4.1 Guidance for corticosteroids tapering for management of immune-related AEs

Reduce prednisone dose by 2.5 to 5.0 mg decrements every 3–7 days until physiologic dose (5 to 7.5 mg of prednisone per day) is reached. Consider to complete tapering over a period of at least 4 weeks. Slower tapering of corticosteroids therapy may be recommended if the adverse event is not showing improvement. Once corticosteroid tapering is achieved at a level of ≤ 10 mg of prednisone/day (or equivalent), PDR001 can be restarted as indicated in the dose modification tables.

6.3.5 Dose modification and management guideline for adverse events suspected to be related to dabrafenib and/or trametinib

Continue PRD001/placebo.

For adverse events of special interest reported **only for dabrafenib and/or trametinib**, general guidelines for dose modification in [Table 6-21](#) should be followed for dabrafenib and trametinib.

In general, if an AE resolves to Grade 1 or baseline at the reduced dose level, and no additional toxicities are seen after 4 weeks of study treatment at the reduced dose, the dose may be increased to the previous dose level.

A dose reduction below 50 mg BID for dabrafenib or below 1 mg QD for trametinib is not allowed. If a dose reduction below 50 mg BID for dabrafenib is required, dabrafenib will be permanently discontinued but these subjects will be allowed to continue trametinib. If a dose reduction below 1.0 mg QD for trametinib is required, then trametinib will be permanently discontinued, but these subjects will be allowed to continue dabrafenib.

[figure not shown]

Table 6-21 General guidelines for dose modification for adverse events suspected to be related to dabrafenib and/or trametinib treatment

Grade	Recommended adverse event management guidelines	Mandatory dose modification requirements
Grade 1 or Grade 2 tolerable	
 Monitor closely. Provide supportive care according to institutional standards. 	
 Continue dabrafenib and trametinib at the same dose level.

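### Four mandatory dose-modification rows order up to three trametinib reductions where Table 6-7 and Section 6.3 allow two, and Section 6.3.2 can be read to give dabrafenib a different outcome

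*Protocol*

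**What the plan says.** **The dose ladder.** Protocol Section 6.3 states: "Three dose reductions for dabrafenib and two dose reductions for trametinib are permitted". Table 6-7 agrees. Dabrafenib goes from 150 to 100, 75 and 50 mg BID. Trametinib goes from 2 to 1.5 and 1.0 mg QD, and its cell for dose level -3 holds only a dash. The table's footnote adds: "Dose reduction below 50 mg BID for dabrafenib and 1.0 mg QD for trametinib are not allowed".

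**The event tables.** In the column of mandatory requirements, these rows order a reduction of both drugs up to the 3rd occurrence and a permanent stop of both at the 4th:

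- Table 6-11, Grade 3 rash: "Once recovered, reduce dabrafenib and trametinib to the next dose level per Table 6-7" (2nd and 3rd occurrence; the 1st also orders a reduction).
- Table 6-12, Grade 3 renal events: "and then reduce dabrafenib and trametinib to the next lower dose per Table 6-7" (2nd and 3rd occurrence; the 1st also orders a reduction).
- Table 6-17, Grade 3/4 neutropenia: "Once recovered, reduce dabrafenib and trametinib to the next dose level" (3rd occurrence; the 1st and 2nd also order a reduction). Febrile neutropenia is referred to the same row.
- Table 6-16, Grade 2 hand-foot reaction: the reduction applies under the condition "No improvement within 7 days or 2nd or 3rd occurrence". A first episode that fails to improve in 7 days therefore makes three.

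**The general sections.** When steps run out, Section 6.3 stops only the drug concerned. Section 6.3.5 says that below the trametinib floor "trametinib will be permanently discontinued, but these subjects will be allowed to continue dabrafenib". Section 6.3.2 says that for toxicities specific to the dabrafenib and trametinib combination "both treatments should be simultaneously dose reduced, interrupted or discontinued with the exceptions shown below". The exceptions it lists are uveitis, retinal vein occlusion, retinal pigment epithelial detachment and LVEF reduction.

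**The concern.** A site that follows the 3rd-occurrence cell literally is told to lower trametinib to a level that Table 6-7 does not have. The same instruction can be carried out for dabrafenib. The cell does not say what then happens to trametinib, and it places the stop of both drugs one occurrence later.

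A site that turns to the general sections can come away with two different outcomes for dabrafenib: continue without trametinib (6.3, 6.3.5), or stop together with it (6.3.2, if that section is taken to govern these events). Treatment after repeated severe toxicity could then depend on which section was read. Dose reductions and dose intensity are the tolerability endpoints in Table 3-1, so uneven handling would also enter the reported figures. The tables remain in use: the Amendment 7 rationale counts 88 Part 3 patients still on treatment.

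**Working it through.** The check is a count of ordered reductions against available levels. No power or alpha formula is involved.

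**Step 1: levels available.** Table 6-7 shows three levels below the start for dabrafenib (100, 75, 50 mg BID) and two for trametinib (1.5, 1.0 mg QD). This reproduces the three and two stated in Section 6.3.

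**Step 2: reductions ordered before the permanent stop, with no re-escalation.** Each row is taken alone; 1 means that a reduction of both drugs is ordered at that occurrence.

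| Row | 1st, 2nd, 3rd | Total | Dabrafenib | Trametinib |
|---|---|---|---|---|
| 6-11 rash Grade 3 | 1, 1, 1 | 3 | 50 mg BID | no level |
| 6-12 renal Grade 3 | 1, 1, 1 | 3 | 50 mg BID | no level |
| 6-17 neutropenia Grade 3/4 | 1, 1, 1 | 3 | 50 mg BID | no level |
| 6-16 hand-foot Grade 2, first episode not improved in 7 days | 1, 1, 1 | 3 | 50 mg BID | no level |
| 6-16 hand-foot Grade 2, first episode improves | 0, 1, 1 | 2 | 75 mg BID | 1.0 mg QD |

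Shortfall = ordered minus available. For trametinib it is 3 - 2 = 1; for dabrafenib it is 3 - 3 = 0. In milligrams, a third trametinib step of the same size would be 2 - 3 × 0.5 = 0.5 mg, below the 1.0 mg floor.

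**Step 3: rows that fit the ladder.** These order at most two reductions: Table 6-9 Grade 3, Table 6-10 Grade 3/4, Table 6-12 Grade 2, Table 6-14 Grade 3/4, Table 6-16 Grade 3, Table 6-17 thrombocytopenia, Table 6-18 intolerable Grade 2 or Grade 3, and Table 6-19 Grades 2 and 3. The mismatch is therefore confined to the four rows in Step 2.

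**Step 4: effect of re-escalation.** Each affected row recommends re-escalation when the Section 6.3.2 criteria are met (4 weeks at the lower dose without recurrence, and clinical benefit). A subject who regained one level before the 3rd occurrence has used 2 - 1 = 1 level. The 3rd reduction then leads to 1.0 mg, which exists. The gap arises only without such a recovery.

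**Step 5: the general sections side by side, for a subject with no trametinib level left.**

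| Section | Scope | Outcome |
|---|---|---|
| 6.3 | all events in 6.3 | only the exhausted drug stops |
| 6.3.5 | events of dabrafenib and/or trametinib | trametinib stops, dabrafenib may continue |
| 6.3.2 | toxicities specific to the dabrafenib and trametinib combination | both drugs reduced, interrupted or discontinued together; rash, renal events, neutropenia and hand-foot reaction are not among the exceptions |

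Sections 6.3 and 6.3.5 agree. Only 6.3.2 can be read differently.

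**The case against.** The strongest reply is that Section 6.3 already settles the matter. It governs every table in 6.3, makes the Table 6-7 steps binding, and says that a subject needing more reductions stops the specific drug concerned. Its unequal limits show that one drug was expected to run out first. The rash and renal cells also refer to Table 6-7. Read together, these texts give a defined result. This largely stands: Section 6.3 is the most direct text, and a careful reader could apply it.

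A reader might infer that three sections give three conflicting answers. The documents do not support that. Sections 6.3 and 6.3.5 agree. Section 6.3.2 is conditional on combination-specific toxicity, offers reduction and interruption as well as discontinuation, and says nothing about exhausted steps. The affected tables sit in Section 6.3.3, on events common to all three drugs, whose introduction warns that its guidance may differ from that for the dabrafenib and trametinib combination. The possible conflict is thus a matter of interpretation.

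A reader might also infer that trametinib always stops one occurrence earlier than the tables show. That fails for any subject who was re-escalated and has a level left.

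What survives is narrower. Applying Section 6.3 means departing from the literal wording of a cell headed as mandatory. Section 6.3.2 is titled as the general instruction for these two drugs, and the affected cells themselves send the reader there for re-escalation. Its exception list does not resolve the scope question either: Table 6-13 (pneumonitis) and Section 6.3.5.8 (thromboembolic events) act on trametinib without dabrafenib, yet neither event is listed.

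**Conclusion.** The point holds in limited form. Three rows always, and a fourth conditionally, order one more trametinib reduction than the protocol's own ladder contains. For subjects not re-escalated between occurrences, the 3rd-occurrence trametinib instruction cannot be carried out. Sections 6.3 and 6.3.5 point to stopping only the exhausted drug; Section 6.3.2 gives dabrafenib a different outcome only if it is read to apply to these events.

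The count rests on three assumptions: each row is taken alone, there is no re-escalation, and there is no earlier reduction for another event. The protocol does not say how many subjects would reach a 3rd occurrence under these conditions. The number is probably small, and no effect on reported dose intensity or discontinuation can be calculated from the document. A reader might infer damage to the efficacy conclusions. Nothing in the document supports that: sample size, power, alpha and the primary endpoint are unaffected. The change should still be made, because these are mandatory dosing instructions and the correction is cheap.

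**What to change.** The sponsor should reconcile the 3rd-occurrence cells for Grade 3 rash (Table 6-11), Grade 3 renal events (Table 6-12) and Grade 3/4 neutropenia (Table 6-17), and the repeated-reduction cell for Grade 2 hand-foot reaction (Table 6-16), with Table 6-7 and Section 6.3. Sections 6.3, 6.3.2 and 6.3.5 should then say the same about what happens to each drug when one has no dose level left, and 6.3.2 should state whether it covers the events in 6.3.3. Which rule applies is the sponsor's clinical decision; this review proposes none.

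The cost is wording in four cells and three sections, carried in a protocol amendment and communicated to sites. No analysis or sample size calculation has to be redone.
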